**UNFORESEEN RISKS:**

Since the study drug is investigational in PD when taken alone or in combination with other medications, there may be other risks that are unknown. All drugs have a potential risk of an allergic reaction, which if not treated promptly, could become life-threatening. Some things that happen during an allergic reaction that could be a sign or symptom of a life-threatening allergic reaction (anaphylaxis) are:

- a rash
- a fast pulse
- sweating
- a feeling of dread
- swelling around the eyes and mouth
- swelling of the throat
- wheezing
- having a hard time breathing
- a sudden drop in blood pressure (making you feel dizzy or lightheaded)

- inability to breathe without assistance

23.4 *If applicable, indicate which research procedures may have risks to an embryo or fetus should the subject be or become pregnant.*

Response:

Lithium therapy is associated with higher rates of birth defects.

23.5 *If applicable, describe risks to others who are not subjects.*

Response: N/A

## 24.0 Potential Benefits to Subjects\*

24.1 *Describe the potential benefits that individual subjects may experience by taking part in the research. Include the probability, magnitude, and duration of the potential benefits. Indicate if there is no direct benefit.*

*NOTE: Compensation **cannot** be stated as a benefit.*

Response:

Possible benefits may include slowing the rate of PD progression. Results from this study may also benefit other PD patients in the future.

## 25.0 Compensation for Research-Related Injury

- ☐ N/A: The research procedures for this study do not present risk of research related injury (e.g. survey studies, records review studies). This section does not apply.

25.1 *If the research procedures carry a risk of research related injury, describe the available compensation to subjects in the event that such injury should occur.*

Response:

Subjects will receive medical treatment if injured or become ill as a result of this study. The PI will explain the treatment options to you and tell you where you can get treatment.

The University at Buffalo makes no commitment to provide free medical care or payment for any unfavorable outcomes that result from your participation in this research. Medical services will be billed at the usual charge and will be the subject's responsibility or that of a third-party payer but subjects will not be precluded from seeking to collect

compensation for injury related to malpractice, fault, or blame on the part of those involved in the research including the University at Buffalo.

By accepting medical care or accepting payment for medical expenses, subjects are not waiving any legal rights.

25.2 *Provide a copy of contract language, if any, relevant to compensation for research related injury.*

*NOTE: If the contract is not yet approved at the time of this submission, submit the current version here. If the contract is later approved with **different language regarding research related injury**, you must modify your response here and submit an amendment to the IRB for review and approval.*

Response: N/A

## 26.0 Economic Burden to Subjects

26.1 *Describe any costs that subjects may be responsible for because of participation in the research.*

*NOTE: Some examples include transportation or parking.*

Response:

Transportation costs.

☐ N/A: This study is not enrolling subjects, or is limited to records review procedures only. This section does not apply.

## 27.0 Compensation for Participation

27.1 *Describe the amount and timing of any compensation to subjects, including monetary, course credit, or gift card compensation.*

Response:

Participants will be reimbursed for parking fees incurred for each of the two MRI scans downtown in the CTRC. Participants will submit receipts to the study team and will be reimbursed by check mailed to their homes. Parking fees will be \$10/MRI visit maximum or \$20 maximum for the entire study.

☐ N/A: This study is not enrolling subjects, or is limited to records review procedures only. This section does not apply.

☐ N/A: There is no compensation for participation. This section does not apply.

## 28.0 Consent Process

28.1 *Indicate whether you will be obtaining consent.*

*NOTE: This does not refer to consent documentation, but rather whether you will be obtaining permission from subjects to participate in a research study. Consent documentation is addressed in Section 27.0.*

- ☒ **Yes** (If yes, Provide responses to each question in this Section)  
☐ **No** (If no, Skip to Section 27.0)

*28.2 Describe where the consent process will take place. Include steps to maximize subjects' privacy.*

Response:

The consent process will occur in a closed-door, examination clinic room at UBMD Neurology.

*28.3 Describe how you will ensure that subjects are provided with a sufficient period of time to consider taking part in the research study.*

*NOTE: It is always a requirement that a prospective subject is given sufficient time to have their questions answered and consider their participation. See "SOP: Informed Consent Process for Research (HRP-090)" Sections 5.5 and 5.6.*

Response:

Potential subjects will be provided with the consent document at least 48 hours prior to the screening visit to ensure adequate time to read and process the entire document.

*28.4 Describe any process to ensure ongoing consent, defined as a subject's willingness to continue participation for the duration of the research study.*

Response:

Subjects will be asked if they wish to continue in the study at each study visit and phone call.

*28.5 Indicate whether you will be following "SOP: Informed Consent Process for Research (HRP-090)." Pay particular attention to Sections 5.4-5.9. If not, or if there are any exceptions or additional details to what is covered in the SOP, describe:*

- *The role of the individuals listed in the application who are involved in the consent process*
- *The time that will be devoted to the consent discussion*
- *Steps that will be taken to minimize the possibility of coercion or undue influence*
- *Steps that will be taken to ensure the subjects' understanding*

Response:

- ☒ We have reviewed and will be following “SOP: Informed Consent Process for Research (HRP-090).”

### ***Non-English Speaking Subjects***

- ☒ **N/A:** This study will not enroll Non-English speaking subjects.  
(Skip to Section 26.8)

28.6 *Indicate which language(s) other than English are likely to be spoken/understood by your prospective study population or their legally authorized representatives.*

*NOTE: The response to this Section should correspond with your response to Section 6.4 of this protocol.*

Response:

28.7 *If subjects who do not speak English will be enrolled, describe the process to ensure that the oral and written information provided to those subjects will be in that language, how you will ensure that subjects are provided with a sufficient period of time to consider taking part in the research study, and any process to ensure ongoing consent. Indicate the language that will be used by those obtaining consent.*

*NOTE: Guidance is provided on “SOP: Informed Consent Process for Research (HRP-090).”*

Response:

### ***Cognitively Impaired Adults***

- ☐ **N/A:** This study will not enroll cognitively impaired adults.  
(Skip to Section 26.9)

28.8 *Describe the process to determine whether an individual is capable of consent.*

Response: After subjects have had adequate time to review the consent and ask questions about the study, they will be asked to give a brief overview of the study procedures. Only subjects that can accurately describe key aspects of the study will be enrolled.

### ***Adults Unable to Consent***

- ☒ N/A: This study will not enroll adults unable to consent.  
(Skip to Section 26.13)

*When a person is not capable of consent due to cognitive impairment, a legally authorized representative should be used to provide consent (Sections 26.9 and 26.10) **and, where possible, assent of the individual should also be solicited** (Sections 26.11 and 26.12).*

28.9 Describe how you will identify a Legally Authorized Representative (LAR). Indicate that you have reviewed the “SOP: Legally Authorized Representatives, Children, and Guardians (HRP-013)” for research in New York State.

*NOTE: Examples of acceptable response includes: verifying the electronic medical record to determine if an LAR is recorded.*

Response:

- ☐ We have reviewed and will be following “SOP: Legally Authorized Representatives, Children, and Guardians (HRP-013).”

28.10 ***For research conducted outside of New York State, provide information that describes which individuals are authorized under applicable law to consent on behalf of a prospective subject to their participation in the research. One method of obtaining this information is to have a legal counsel or authority review your protocol along with the definition of “legally authorized representative” in “SOP: Legally Authorized Representatives, Children, and Guardians (HRP-013).”***

Response:

28.11 Describe the process for ***assent of the adults***:

- *Indicate whether assent will be obtained from all, some, or none of the subjects. **If some, indicate which adults will be required to assent and which will not.***

Response:

- ***If assent will not be obtained from some or all subjects, provide an explanation of why not.***

Response:

28.12 Describe whether ***assent of the adult*** subjects will be documented and the process to document assent.

*NOTE: The IRB allows the person obtaining assent to document assent on the consent document using the “Template Consent Document (HRP-502)” Signature Block for Assent of Adults who are Legally Unable to Consent.*

Response:

***Subjects who are not yet Adults (Infants, Children, and Teenagers)***

- ☒ **N/A:** This study will not enroll subjects who are not yet adults.  
(Skip to Section 27.0)

**28.13** Describe the criteria that will be used to determine **whether a prospective subject has not attained the legal age for consent to treatments or procedures involved in the research** under the applicable law of the jurisdiction in which the research will be conducted (**e.g., individuals under the age of 18 years**). For research conducted in NYS, review “SOP: Legally Authorized Representatives, Children, and Guardians (HRP-013)” to be aware of which individuals in the state meet the definition of “children.”

*NOTE: Examples of acceptable responses include: verification via electronic medical record, driver’s license or state-issued ID, screening questionnaire.*

Response:

**28.14** **For research conducted outside of New York State**, provide information that describes which persons have not attained the legal age for consent to treatments or procedures involved the research, under the applicable law of the jurisdiction in which research will be conducted. One method of obtaining this information is to have a legal counsel or authority review your protocol along the definition of “children” in “SOP: Legally Authorized Representatives, Children, and Guardians (HRP-013).”

Response:

**28.15** Describe whether parental permission will be obtained from:

Response:

- ☐ One parent even if the other parent is alive, known, competent, reasonably available, and shares legal responsibility for the care and custody of the child.
- ☐ Both parents unless one parent is deceased, unknown, incompetent, or not reasonably available, or when only one parent has legal responsibility for the care and custody of the child.

- ☐ Parent permission will not be obtained. A waiver of parent permission is being requested.

*NOTE: The requirement for parent permission is a protocol-specific determination made by the IRB based on the risk level of the research. For guidance, review the "CHECKLIST: Children (HRP-416)."*

28.16 Describe whether permission will be obtained from individuals **other than parents**, and if so, who will be allowed to provide permission. Describe your procedure for determining an individual's authority to consent to the child's general medical care.

Response:

28.17 Indicate whether assent will be obtained from all, some, or none of the **children**. If assent will be obtained from some children, indicate which children will be required to assent.

Response:

28.18 When assent of children is obtained, describe how it will be documented.

Response:

## 29.0 Waiver or Alteration of Consent Process

***Consent will not be obtained, required information will not be disclosed, or the research involves deception.***

- ☒ N/A: A waiver or alteration of consent is not being requested.

29.1 If the research involves a waiver or alteration of the consent process, please review the "CHECKLIST: Waiver or Alteration of Consent Process (HRP-410)" to ensure that you have provided sufficient information for the IRB to make the determination that a waiver or alteration can be granted.

*NOTE: For records review studies, the first set of criteria on the "CHECKLIST: Waiver or Alteration of Consent Process (HRP-410)" applies.*

Response:

29.2 If the research involves a waiver of the consent process for planned emergency research, please review the "CHECKLIST: Waiver of Consent for Emergency Research (HRP-419)" to ensure you have provided sufficient information for the IRB to make these determinations. Provide any additional information necessary here:

Response:

### 30.0 Process to Document Consent

- ☐ N/A: A Waiver of Consent is being requested.  
(Skip to Section 29.0)

30.1 Indicate whether you will be following “SOP: Written Documentation of Consent (HRP-091).” If not or if there are any exceptions, describe whether and how consent of the subject will be obtained including whether or not it will be documented in writing.

NOTE: If your research presents no more than minimal risk of harm to subjects and involves no procedures for which written documentation of consent is normally required outside of the research context, the IRB will generally waive the requirement to obtain written documentation of consent. This is sometimes referred to as ‘verbal consent.’ Review “CHECKLIST: Waiver of Written Documentation of Consent (HRP-411)” to ensure that you have provided sufficient information.

 If you will document consent in writing, attach a consent document with your submission. You may use “TEMPLATE CONSENT DOCUMENT (HRP-502)”. If you will obtain consent, but not document consent in writing, attach the script of the information to be provided orally or in writing (i.e. consent script or Information Sheet).

Response:

- ☒ We will be following “SOP: Written Documentation of Consent” (HRP-091).

### 31.0 Multi-Site Research (Multisite/Multicenter Only)\*

- ☒ N/A: This study is not an investigator-initiated multi-site study. This section does not apply.

31.1 Indicate the total number of subjects that will be enrolled or records that will be reviewed across all sites.

Response:

31.2 If this is a multi-site study **where you are the lead investigator**, describe the processes to ensure communication among sites, such as the following. See “WORKSHEET: Communication and Responsibilities (HRP-830).”:

- All sites have the most current version of the IRB documents, including the protocol, consent document, and HIPAA authorization.
- All required approvals have been obtained at each site (including approval by the site’s IRB of record).

- *All modifications have been communicated to sites, and approved (including approval by the site's IRB of record) before the modification is implemented.*
- *All engaged participating sites will safeguard data as required by local information security policies.*
- *All local site investigators conduct the study appropriately in accordance with applicable federal regulations and local laws.*
- *All non-compliance with the study protocol or applicable requirements will be reported in accordance with local policy.*

Response:

31.3 *Describe the method for communicating to engaged participating sites (see "WORKSHEET: Communication and Responsibilities (HRP-830)"):*

- *Problems (inclusive of reportable events)*
- *Interim results*
- *Study closure*

Response:

31.4 *If this is a multicenter study **where you are a participating site/investigator**, describe the local procedures for maintenance of confidentiality. (See "WORKSHEET: Communication and Responsibilities (HRP-830).")*

- *Where and how data or specimens will be stored locally?*
- *How long the data or specimens will be stored locally?*
- *Who will have access to the data or specimens locally?*
- *Who is responsible for receipt or transmission of the data or specimens locally?*
- *How data and specimens will be transported locally?*

Response:

31.5 *If this is a multicenter study and subjects will be recruited by methods not under the control of the local site (e.g., call centers, national advertisements) describe those methods. Local recruitment methods are described elsewhere in the protocol.*

- *Describe when, where, and how potential subjects will be recruited.*
- *Describe the methods that will be used to identify potential subjects.*
- *Describe materials that will be used to recruit subjects. (Attach copies of these documents with the application. For*

*advertisements, attach the final copy of printed advertisements. When advertisements are taped for broadcast, attach the final audio/video tape. You may submit the wording of the advertisement prior to taping to preclude re-taping because of inappropriate wording, provided the IRB reviews the final audio/video tape.)*

Response:

### 32.0 Banking Data or Specimens for Future Use\*

- ☐ N/A: This study is not banking data or specimens for future use or research outside the scope of the present protocol. This section does not apply.

32.1 *If data or specimens will be banked (stored) for **future use, that is, use or research outside of the scope of the present protocol**, describe where the data/specimens will be stored, how long they will be stored, how the data/specimens will be accessed, and who will have access to the data/specimens.*

*NOTE: Your response here must be consistent with your response at the “What happens if I say yes, I want to be in this research?” Section of the Template Consent Document (HRP-502).*

Response:

Blood specimens will be stored in a locked freezer at UBMD Neurology, [name] and in the laboratory of [name] on the 5th floor of the CTRC. The specimens will be stored indefinitely. Only the PI and [name] will have access to the stored specimens. MRI scan data will also be stored indefinitely on the password-protected BNAC computer servers.

32.2 *List the data to be stored or associated with each specimen.*

Response:

Subject ID, DOB, date and time collected.

32.3 *Describe the procedures to release banked data or specimens for future uses, including: the process to request a release, approvals required for release, who can obtain data or specimens, and the data to be provided with specimens.*

Response:

Any party besides the PI will need to obtain approval from the PI prior to release of any blood specimens. The request will need to have scientific merit, in the PI's opinion.

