### 3.0 Scientific Endpoints\*

2.1 Describe the scientific endpoint(s), the main result or occurrence under study.

*NOTE: Scientific endpoints are outcomes defined before the study begins to determine whether the objectives of the study have been met and to draw conclusions from the data. Include primary and secondary endpoints. Some example endpoints are: reduction of symptoms, improvement in quality of life, or survival. Your response should **not** be a date.*

Response:

Primary Outcome Measures:

- Clinical Adverse Events assessed at screening, Baseline (BL), and week 24 as well as during a phone call at week 12.
- Blood safety laboratory assessments at screening and week 24 (CBC, CMP, TSH, calcium, ESR, urate, HgA1C and trough serum lithium performed by Kaleida Laboratory Services).
- MRI-based disease-progression biomarkers at BL and week 24:
  - Posterior substantia nigra (pSN), nucleus basalis of Meynert (nbM) and dorsomedial nucleus of the thalamus (DMN-T) free water (FW) levels.
- Blood-based therapeutic targets at BL and week 24:
  - PBMC Nurr1 mRNA levels by real-time polymerase chain reaction (PCR).

Secondary Outcome Measures at BL and week 24:

- PBMC SOD-1 mRNA levels by PCR, PBMC phosphorylated (p) and total (t) levels of pS9 and t-GSK-3 $\beta$ ; pThr308, pS473 and t-Akt (both t and the ratio of p/t will be used for each data point) and plasma interleukin-6 (IL-6) levels by ELISA.
- Trough, steady-state plasma lithium levels assessed by the UB Chemistry Instrument Center utilizing an inductively coupled plasma mass spectrometer (ICPMS) at BL and week 24.
- Clinical Assessments at BL and week 24:
  - Movement Disorder Society-Unified Parkinson's Disease Rating Scale (MDS-UPDRS), Part III (Motor Examination).
  - Parkinson's Anxiety Scale.
  - Geriatric Depression Scale-15.
  - Fatigue Severity Scale.
  - Insomnia Severity Index.
  - Parkinson's Disease Questionnaire-8.
- Montreal Cognitive Assessment (MoCA) at screening and week 24.

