## 5.0 Study Design\*

*5.1 Describe and explain the study design (e.g. case-control, cross-sectional, ethnographic, experimental, interventional, longitudinal, observational).*

Response:

We will enroll 15 additional PD patients within five months. Eligible patients will have PD for <4 years diagnosed by a movement disorder specialist (Drs. [name] or [name]), be 45-80 years old, have normal thyroid and renal function at the screening visit, have no previous exposure to lithium therapy, have no history of brain surgery, have no hx of brain imaging findings suggesting another neurological condition besides PD, have no use of tobacco or THC products for >1 year, have stable PD medications for >30 days without current need for adjustments in the investigator's opinion, and have stable psychiatric and diuretic medications for >60 days with no anticipated need for changes for at least 24 weeks.

All patients will receive medium-dose lithium aspartate therapy (30-45mg/day) for 24 weeks ensuring that the study will be completed within 12 months. The following dose titration will be used in order to minimize side effects: 10mg bid x 1 week, then 15mg bid x 1 week, then 20mg bid x 2 weeks, then 20mg qAM and 25mg qhs thereafter. Patients will be contacted weekly over the first 4-6 weeks to assess for side effects that are likely to be due to lithium, such as sedation, dizziness or confusion. If side effects occur and are bothersome to the patient, the dose will be decreased incrementally to a minimum of 30mg/day. Such a design will enable identification of the maximum tolerated dose for study in a future trial and maximize the number of patients receiving the most promising dose (45mg/day) identified in the previous pilot clinical trial. Blood-based biomarkers and MRIs will be assessed at baseline and 24 weeks.

The primary blood-based biomarker outcome measure will be change in PBMC Nurr1 mRNA expression from baseline to 24 weeks, which will be compared with the data from the three control PD patients from the pilot study using ANCOVA. PBMC mRNA expression will be assessed by quantitative real-time PCR using TaqMan probes to match the pilot study's methodology. Based on the

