## **20.0 Confidentiality\***

### **A. Confidentiality of Study Data**

*Describe the local procedures for maintenance of confidentiality of **study data** and any records that will be reviewed for data collection.*

*20.1 A. Where and how will all data and records be stored? Include information about: password protection, encryption, physical controls, authorization of access, and separation of identifiers and data, as applicable. Include physical (e.g. paper) **and** electronic files.*

Response: A study binder will be assembled for each subject that will contain all of the non-biomarker data collected. However, the forms linking subjects' personal identifiable information to their study ID numbers will be kept in a separate folder. This folder and all study binders will be stored in a locked room in a locked cabinet at the study site. These data as well as biomarker data will be entered into an excel file on the coordinator's password protected computer located in this same locked room. The excel file will only contain subject ID numbers and no personal identifiable information.

*20.2 A. How long will the data be stored?*

Response: Indefinitely.

*20.3 A. Who will have access to the data?*

Response: The study coordinator and PI.

*20.4 A. Who is responsible for receipt or transmission of the data?*

Response: The study PI.

*20.5 A. How will the data be transported?*

Response: Electronically.

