## **B. Confidentiality of Study Specimens**

*Describe the local procedures for maintenance of confidentiality of **study specimens**.*

- ☐ **N/A:** No specimens will be collected or analyzed in this research.  
(Skip to Section 19.0)

*20.6 B. Where and how will all specimens be stored? Include information about: physical controls, authorization of access, and labeling of specimens, as applicable.*

Response: Subjects' blood samples will be labeled with their ID#, DOB, date and time of collection. Some samples will be stored in a locked freezer at the study site until the time of analysis. Some samples will be immediately transported to the laboratory of [name], 5th floor CTRC. MRI scans will be labeled with subject ID#, DOB, date and time of collection.

*20.7 B. How long will the specimens be stored?*

Response: Indefinitely

*20.8 B. Who will have access to the specimens?*

Response: The study coordinator and PI, [name], and the technician at UB's Chemistry Instrument Center ([name]).

*20.9 B. Who is responsible for receipt or transmission of the specimens?*

Response: The PI.

*20.10 B. How will the specimens be transported?*

Response: By local courier to [name]'s laboratory and UB's Instrument Center.

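### Blood sample labels let the laboratory measuring Nurr1 tell baseline from Week 24, and the plan provides no masking to time point and no paired, random-order assay

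*Combined protocol and SAP*

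**What the plan says.** The label rule for study samples is in section 20.6: "blood samples will be labeled with their ID#, DOB, date and time of collection". The same section says that some samples wait in a freezer at the study site, while for others "Some samples will be immediately transported to the laboratory of" the laboratory on the 5th floor of the research centre. It does not say which samples take which route.

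Section 5.1 fixes the treatment ("All patients will receive medium-dose lithium aspartate therapy (30-45mg/day) for 24 weeks") and the assay ("PBMC mRNA expression will be assessed by quantitative real-time PCR using TaqMan probes"). Section 3.0 lists PBMC Nurr1 mRNA as a primary measure under the heading "Blood-based therapeutic targets at BL and week 24". Section 5.1 makes the primary blood outcome the change between these two visits, to be compared by ANCOVA with three untreated pilot patients.

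Section 32.2 lists the data kept with each banked specimen: "Subject ID, DOB, date and time collected". Section 32 concerns "use or research outside of the scope of the present protocol", so it does not govern the Nurr1 assay itself. Section 20.1 says of the data file: "The excel file will only contain subject ID numbers and no personal identifiable information".

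**The concern.** Open-label describes what patients and clinicians know. It does not require the assay laboratory to know which visit a sample came from. Because the outcome is a within-patient change, visit order plays the part inside each pair that treatment assignment plays in a parallel-group trial. The hoped-for result has a direction: Nurr1 should rise on lithium.

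Real-time PCR is read by an instrument, but people still decide whether to rerun a sample, which replicates to drop and which samples share a run. The plan states no rules for these steps, and section 19.3, on quality control of collected data, is answered as not applicable. If such decisions are made with visit order in view, they can lean towards an increase. If the two samples of a pair are run months apart, run-to-run variation also enters the change. The Nurr1 result is meant to support an application for a larger randomised trial.

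**Working it through.** **1. The plan's own figure.** The only calculation attached to this outcome is in section 5.1: two patients suffice, given an SD of 22%, an effect of 540% (679% − 139%), 95% power and two-sided alpha 0.05. The normal approximation gives 2 × [22 × (1.960 + 1.645) / 540]² = 0.043 per arm, which rounds up to 1. Two per arm is the smallest equal size that allows a t test, and its power exceeds 0.999. The figure reproduces, but it says nothing about assay handling, and this point does not depend on it.

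**2. What the label reveals.**

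| Input | Value | Section |
|---|---|---|
| Label | ID, birth date, collection date and time | 20.6 |
| Nurr1 samples per patient | 2 (baseline, Week 24) | 3.0, 12.1 |
| New patients planned on lithium | 15 of 15 | 5.1 |
| Outcome | Week 24 minus baseline | 5.1 |

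ID groups the two samples of a patient and the date orders them, so the later sample is identified with certainty. With a random code replacing these items, and no other clue, a guess is right half the time per pair. The chance of ordering all 15 pairs correctly by guessing is 0.5¹⁵ ≈ 0.00003. Birth date adds nothing to the ordering.

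**3. Is there a safeguard elsewhere?** I checked sections 5.1 (assay), 12.1 (visits), 19.1 and 19.3 (analysis and quality control) and 20.6 to 20.10 (specimens). None provides for recoding, masking to visit, running a pair together, random order, or rules for reruns and exclusions. None says that the laboratory is told the visit either.

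**4. Would the comparison cancel a shift?** On the log scale, let b(new) and b(control) be the average within-pair assay shifts in the new patients and the pilot controls. The estimated difference then carries a bias of b(new) − b(control). It cancels only if the two shifts are equal. The documents do not say how the pilot pairs were labelled or batched, so this cannot be assumed.

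**5. Scale, not evidence.** Assume full PCR efficiency, that is, doubling per cycle. A relative shift of s cycles multiplies the Week 24 to baseline ratio by 2^s.

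- s = 0.5: 2^0.5 − 1 = 0.41, or +41%.
- s = 1: 2^1 − 1 = 1.00, or +100%.

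For comparison, I convert the pilot group means in section 4.1 as if each were a single ratio.

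- Untreated controls, +139%: log2(2.39) = 1.26 cycles.
- Medium dose, +679%: log2(7.79) = 2.96 cycles.

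The gap is 2.96 − 1.26 = 1.70 cycles. A shift of 0.5 to 1 cycle would be a visible part of that gap but would not account for all of it. No passage indicates that a shift of either size occurs.

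**The case against.** The strongest reply is that this is a 15-patient, open-label, proof-of-concept study with an instrument-read assay. The laboratory may know that every new patient takes lithium whatever the tube says. Samples delivered fresh reveal their date on arrival, so a new tube label would not hide it. The larger limit on the Nurr1 result, three non-concurrent controls, would be untouched.

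Much of this stands. The label adds only the time point, the room for bias is limited to a few discretionary steps, and for fresh samples recoding has to take place after processing. None of it removes the point: knowing that all patients are treated does not favour one tube over the other, whereas knowing the visit does.

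A reader might also infer more than the text supports:

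- **That the laboratory is unmasked.** No passage says that it is told visit or treatment. The supported statement is that masking is not provided for and that the label would defeat it.
- **That every later sample is on lithium.** Section 22.2 asks withdrawn subjects to undergo the Week 24 procedures at a final visit, and some may have stopped by then.
- **That the analysis could never uncover a bias.** Specimens are kept indefinitely, so a coded re-assay could check the result if material remains.
- **That the birth date on the tube contradicts section 20.1.** The sentence quoted from there concerns the data file only; specimens have their own section.

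**Conclusion.** The point holds in a limited form. The stated label rule makes the visit order of every pair visible to the laboratory measuring a primary outcome, and the plan contains neither masking to time point nor paired, random-order assay. This is a weakness in design that is cheap to remove. It is not evidence that Nurr1 results are or will be biased. The size and even the presence of a bias are unknown; the cycle figures show only how a shift would translate, and they assume full PCR efficiency.

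The conclusion also assumes that some rerun, exclusion or batching decisions are made by people who see the labels, which the documents neither state nor rule out. Birth date is a privacy matter, separate from masking. Section 32.3 does not say whether it travels with released specimens.

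**What to change.** In section 20.6:

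- Have someone outside the assay step relabel the stored, processed aliquots (RNA, lysate, plasma) with a random code before assay. The coordinator is an example, and section 20.8 already gives that role access to specimens. Include material that first reached the laboratory fresh.
- Assay each patient's two aliquots in the same run, in random order, with the same TaqMan method as the pilot.
- Write down the rerun and replicate-exclusion rules beforehand.
- Keep the key outside the laboratory and release it only when results, including reruns and exclusions, are final.

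This assumes that processed material can be stored until both visits are available, which the laboratory should confirm.

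The costs are a key list and a relabelling step, loss of birth date as a second identity check, and deferral of the baseline assay until Week 24. Batching may also differ from that of the pilot controls; the report should describe any such difference. No extra patients, visits or blood are needed.

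Separately, and for privacy only, remove the birth date from banked specimens released under section 32.3.
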